VRT-DIBH	VRT-assisted DIBH

STUDY SCHEMA

STUDY SUMMARY

Title	VisionRT-based Deep Inspiration Breath-hold (DIBH) Respiratory Motion Management Strategy, A Pilot Study for Thoracic and Abdominal Tumors Stereotactic Body Radiotherapy
Short Title	VRT-DIBH for Thoracic and Abdominal Cancer SBRT
Protocol Number	STU 022017-075
Phase	Pilot
Methodology	Prospective study with retrospective data analysis
Study Duration	2 year
Study Center(s)	Single-center
Objectives	To prove the feasibility of using VRT-DIBH for thoracic and abdominal tumors SBRT
Number of Subjects	10
Diagnosis and Main Inclusion Criteria	
 Patients with tumors in thorax and abdomen Patients are eligible for SBRT
Study Product(s), Dose, Route, Regimen	No therapeutic intervention – per SOC
Duration of administration	Per SOC
Statistical Methodology	Descriptive statistics will be computed to investigate the feasibility of the trial.

1.0 BACKGROUND AND RATIONALE

1.1 Background

Respiratory motion affects all tumor sites in the thorax and abdomen. The disease of most prevalence and relevance for motion-management needed radiotherapy are lung and liver cancer. Lung cancer is the leading cause of cancer-related mortality in the United States. During 2016, an estimated 224,390 new cases of lung cancer are diagnosed, representing 13% of all cancer patients¹, and an estimated 158,080 deaths of lung cancer were expected¹. The five-year survival rate for all stages combined is 17.7%, lower than many other leading cancer sites, such as the colon (64.4%), breast (89.7%) and prostate (98.9%)². Liver cancer is the 10th most common cancer. In 2016, an estimated 39,230 adults (28,410 men and 10,820 women) in the United States will be diagnosed with primary liver cancer¹. The 5-year survival rate of liver cancer is 17%².

Stereotactic body radiotherapy (SBRT) is a therapeutic paradigm developed in the mid 1990's. It administers very high, biological potent doses in few fractions (1 - 5 fractions) using unique beam arrangements and special immobilization equipment. It has demonstrated excellent local control in patients with inoperable non-small cell lung cancer (NSCLC)³ and liver cancer⁴.

Respiratory motion causes significant geometric and dosimetric uncertainties in lung and upper abdomen cancer radiotherapy treatment simulation, planning, and delivery⁵. These uncertainties are particularly large in SBRT, potentially leading to significant collateral toxicity⁶⁻⁸ when using large beam apertures or, conversely, potential marginal miss with very small apertures. Researchers and clinicians have been investigating respiratory motion-management techniques for over a decade.^{9, 10} A variety of motion management strategies have been explored and implemented for clinical use, including motion-encompassing methods [e.g. 4D CT and ITV (internal target volume) approach], abdominal compression techniques to decrease motion amplitude, breath-holding methods, respiratory-gating techniques, and real-time tumor-tracking methods. All of these techniques aim to mitigate dosimetric uncertainties induced by respiratory motion by either restricting or compensating for motion.

1.2 DIBH and Active Breathing Coordinator (ABC)

Among various respiratory motion management techniques, deep-inspiration breath-hold (DIBH) technique has been developed and applied in lung and liver SBRT.^{11, 12} DIBH has shown advantages for treating thoracic and abdominal tumors because it can significantly reduce respiratory tumor motion and changes internal anatomy in way that often protects critical normal tissues.

There are several ways to assist DIBH during radiation treatments. One common way is by using a commercially available system Active Breathing Coordinator (ABC; Elekta, Crawley, UK) device. The ABC system has a digital spirometer that records real time breathing. When the patient inspires to a preset DIBH level, a balloon valve is inflated so as to prevent the patient from breathing out and thereby maintain a consistent chest wall expansion with each DIBH. A nose clip prevents air leakage. The therapist monitors the

respiratory cycle and DIBH signals on the screen during the radiation delivery. When the patient depresses a handheld thumb switch, treatment is stopped and valve opens so breathing can resume normally again. Dosimetric advantages of cardiac sparing using DIBH ABC technique have been shown.^{13, 14} Currently, UTSW lung and liver SBRT and left breast conventional irradiation are used ABC assisted DIBH (ABC-DIBH) for respiratory motion management.

Several studies have pointed out potential drawbacks of the ABC system. For example, even though the patient's tidal volume remains consistent with ABC, different breathing maneuvers (abdominal versus thoracic breathing) can cause for variations in breath-hold.¹⁵ They reported that for the same vital capacity, abdominal and thoracic breathing led to an average difference of chest wall expansion of 1.9 cm. Remouchamps *et al.* also showed that that overshoot can occur with ABC device where the patient can inhale a larger air volume than the pre-determined set limit.^{13, 16} More recently, Mittauer *et al.* showed through using an optical surface-tracking system to monitor ABC-assisted DIBH, that large positional variations can occur in some patients due to their different breath hold techniques¹⁷ and concluded that optical tracking system is a valuable tool for ABC-assisted DIBH.

1.3 VRT and VRT-DIBH

A more recent competing technology for implementing the DIBH technique is real-time surface photogrammetry using the AlignRT system (Vision RT Ltd., London, UK). AlignRT system use non-ionization near infrared light to track patient surface motion. The system has one projector projecting near infrared optical pattern on patient surface. The optical pattern is imaged by optical cameras (two per pod) at ~25 Hz. The user selects a region-of-interest (ROI) on the surface and the software calculates and displays the real-time position in six degrees (3 translations and 3 rotations) in real-time. Once the patient has matched the pre-determined DIBH position (within threshold accuracy), the radiation beam is enabled to be turned on for treatment.

Currently, VRT-DIBH has already applied to left breast radiotherapy to spare lung and heart. Compared to ABC-DIBH, VRT-DIBH has several potential advantages:

1. VRT monitors patient (surface) position in addition to DIBH signal, while ABC only check the tidal volume, which can remain the same even if the patient shifts slightly on the couch;
2. VRT is more cost effective, as patient tubing needs to be replaced daily for ABC;
3. VRT potentially has advantage on patient compliance, as with ABC breath is forced impeded while with VRT breath-hold is voluntary.

In this study, we renovate the established DIBH motion management strategy by adopting AlignRT system. The purpose of this study is to develop, validate, and prove the feasibility of VRT-DIBH technique for lung and liver SBRT.

2.0 STUDY OBJECTIVES

2.1 Primary Objectives

2.1.1 To investigate the feasibility of applying VRT-DIBH to lung/liver cancer SBRT

2.2 Secondary Objectives

2.2.1 To determine planning target volume margin by investigating tumor residual motion in VRT-DIBH

2.2.2 To determine VRT surface monitoring threshold by investigating inter/intra VRT-DIBH patient surface stability/reproducibility/sensitivity

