2.3.2 Treatment time

2.4 Endpoints

2.4.1 VRT-DIBH feasibility

2.4.2 To determine target margin in VRT-DIBH lung/liver SBRT

2.4.3 To determine threshold used for surface monitoring in VRT-DIBH assisted lung/liver SBRT

3.0 PATIENT ELIGIBILITY

Eligibility waivers are not permitted. Subjects must meet all of the inclusion and exclusion criteria to be registered to the study. Study treatment may not begin until a subject is registered.

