DIBH qualified patient will experience one high-resolution CT scan as SOC and additional lower dose CT scans to further investigate inter-DIBH patient surface and tumor position stability and repeatability.

1. Spirometer will be used to select DIBH level and monitor DIBH status during CT simulation. One SOC high-resolution CT will be acquired in single DIBH duration. Within 10 minute, a low-resolution/low-dose CT image in single DIBH duration will be acquired. This study is to quantify inter-DIBH tumor position and patient surface repeatability.
2. Patient will then be scanned using a lower dose CT protocol with DIBH level set at $\pm 10\%$ deviated from the selected DIBH level. This study is to find the correlation between DIBH level and tumor position /chest-abdomen surface level.

The SOC DIBH CT scan will be transferred to Eclipse treatment planning system for treatment planning. Tidal volume measured by spirometer and DIBH surface from CT image will be used as a reference surface for patient treatment initial setup. CBCT will be acquired before each fractional treatment for the patient alignment before beam delivery.

During the treatment delivery, patient will perform DIBH while AlignRT system monitors patient surface. As a pilot study, we will also use spirometer to monitor patient breath-hold tidal volume, and imaging acquired in any two DIBH periods to quantify inter- and intra- DIBH tumor position variation. Following our SBRT treatment protocol, patient will get CBCT scan before the last beam delivery. We will follow the same protocol to acquire CBCT images. These CBCT images will be used to evaluate treatment dose variation to quantify treatment delivery accuracy.

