5.2.2 Tumor motion evaluation and target volume delineation

On the acquired four different DIBH CTs, gross tumor volume (GTV) will be contoured by an appropriately trained physician. Tumor center point (center of mass) will be the identified and used for motion evaluation. Both inter- and intra- motion amplitude will be analyzed and margins will be estimated. The acquired high-resolution DIBH CT will be used as a primary image for planning. Physician will expand the GTV to PTV by adding proper size margins.

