5.2.5 Daily treatment

- Patient will be positioned with vac lock bag in stereotactic body frame and setup with stereotactic coordinates recorded during simulation;
- Setup DIBH tidal volume use spirometer to reproduce simulated tidal volume;
- Initial setup patient position with AlignRT system using CT surface;
- Patient will receive a CBCT scan and align to simulated CT images;
- Right after CBCT alignment, AlignRT system will acquire a new surface image for treatment monitoring;
- Treatment delivery follows routine SBRT treatment, with one CBCT check before and one CBCT before last beam (not during treatment beam delivery).

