5.2.8 Post-Radiation analysis

- Analyze recorded daily AlignRT treatment setup delta values
- Analyze recorded daily position shift using CBCT alignment
- Analyze recorded daily AlignRT treatment delta values, investigate surface stability and reproducibility
- Delineate tumor on recorded CBCT images and investigate the position error
- Project treatment beams on CBCT images and recalculate dose with CBCT images. Evaluate dose difference between the planned and the delivered.
- Treatment time analysis

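### The PTV margin is linked only to tumor motion, taken from simulation CTs; the treatment-day position error that is collected is not linked to it

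*Combined protocol and SAP*

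**What the plan says.** Objective 2.2.1 is "To determine planning target volume margin by investigating tumor residual motion in VRT-DIBH". Residual motion is not defined. The matching endpoint, 2.4.2, is "To determine target margin in VRT-DIBH lung/liver SBRT", with no error source and no formula.

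Section 5.2.2 is the only procedure that connects data to a margin. It contours the GTV on four DIBH CTs, uses the center of mass to evaluate motion, and states: "Both inter- and intra- motion amplitude will be analyzed and margins will be estimated". By 4.1 and 5.2.1, those four scans are the planning CT, a low-dose repeat at the same level within 10 minutes, and two low-dose scans set 10% above and below that level. Section 4.1 gives the two kinds of repeat different purposes: repeatability for the same-level scan, and the relation between breath level and position for the offset scans. Section 5.2.2 does not carry that distinction over. For the individual plan it says "Physician will expand the GTV to PTV by adding proper size margins".

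Treatment-day data are planned elsewhere. Section 4.1 calls for "imaging acquired in any two DIBH periods to quantify inter- and intra- DIBH tumor position variation" during delivery. Section 5.2.5 has a CBCT for alignment and another before the last beam. Section 5.2.8 lists "Analyze recorded daily position shift using CBCT alignment" and "Delineate tumor on recorded CBCT images and investigate the position error". Section 6.3 evaluates tumor position accuracy on all recorded CBCTs. None of these mentions the margin.

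**The concern.** A GTV-to-PTV margin has to cover where the tumor is, relative to plan, when the beam is on. Hold-to-hold motion is one part of that. What remains after CBCT alignment, and change since simulation that alignment does not remove, are others. Four scans from one simulation visit contain neither. The protocol itself treats patient position as separate from breath level: section 1.3 notes that tidal volume can stay the same while the patient moves on the couch.

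Two of the four scans are also displaced on purpose. If they enter the motion amplitude, it mixes natural variation with an experimental offset.

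At stake is the margin that the pilot reports under 2.4.2. Section 1.1 names both hazards of getting the aperture wrong: collateral toxicity if it is too large and marginal miss if it is too small.

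**Working it through.** **Step 1. Which data are tied to the margin.**

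| Data | When | Section | Linked to margin? |
|---|---|---|---|
| Tumor residual motion (undefined) | not stated | 2.2.1 | yes |
| Center of mass on four DIBH CTs | simulation | 5.2.2 | yes |
| Tumor imaging in two holds | treatment | 4.1 | no |
| CBCT alignment shifts | treatment | 5.2.8 | no |
| Tumor position error on CBCT | treatment | 5.2.8, 6.3 | no |

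**Step 2. Inputs.** From the protocol: 10 patients (6.0, 6.2) and four CTs at relative levels 0, 0, +10% and -10% (5.2.1). It states no margin, formula or SD, so there is no figure of the plan to reproduce. The following are my assumptions, for illustration only: motion SD m = 1 to 2.5 mm; SD of the residual after alignment s = 0.5 to 2 mm, independent of motion; tumor shift at the offset levels d = 1 to 3 mm; margin proportional to the SD of position error.

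**Step 3. Effect of leaving out the alignment residual.** Total SD = sqrt(m² + s²), so the shortfall is 1 - m/sqrt(m² + s²).
- m = 2.5, s = 0.5: total 2.55, shortfall 2%.
- m = 2, s = 1: total 2.24, shortfall 11%.
- m = 1, s = 2: total 2.24, shortfall 55%.

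**Step 4. Effect of pooling the offset CTs.** Four positions with offsets 0, 0, +d, -d have expected sample variance m² + 2d²/3. With m = 1.5:
- d = 1: sqrt(2.25 + 0.67) = 1.71, ratio 1.14.
- d = 2: sqrt(2.25 + 2.67) = 2.22, ratio 1.48.
- d = 3: sqrt(2.25 + 6) = 2.87, ratio 1.91.

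**Step 5. Both together.** With m = 1.5 and s = 1, the total SD to be covered is sqrt(2.25 + 1) = 1.80. The pooled simulation SD is 1.71 at d = 1 (1.71/1.80 = 0.95, too low) and 2.87 at d = 3 (2.87/1.80 = 1.59, too high). The two effects cancel when 2d²/3 = s², that is d = 1.22s. The sign depends on quantities that the documents do not give.

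**Step 6. Precision.** The 95% interval for a between-patient SD, with one normal value per patient, runs from sqrt((n-1)/χ²(0.975)) to sqrt((n-1)/χ²(0.025)) times the estimate.
- n = 10: sqrt(9/19.02) = 0.69 to sqrt(9/2.70) = 1.83.
- n = 5, the number finishing if exactly the 50% in section 6.0 is met: sqrt(4/11.14) = 0.60 to sqrt(4/0.484) = 2.87.

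This is a separate matter from bias, but a reader of the reported margin needs it.

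**The case against.** Nothing in the protocol says that the margin rests on motion and nothing else. Residual motion is undefined and could be meant to include position error remaining after alignment. Section 5.2.2 also speaks of motion within a hold. Section 4.1 describes the planning CT and its same-level repeat as each taken in a single hold, so the CT set cannot readily supply that. The authors may therefore have had the motion-assessment session or the treatment-day imaging in mind. The treatment-day errors are collected and will be analyzed. Alignment before each fraction is meant to remove much of the day-to-day change, so the omitted term could be small. And this is a secondary, descriptive output of a 10-patient pilot.

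Much of this stands. A reader might infer that CBCT error is excluded by design; the text is silent, which is not the same. A reader might also infer that the margin will be too small. Step 5 shows that this does not follow, and the percentages in Step 3 rest wholly on assumed SDs. It is also right that adding hold-to-hold variation to the error on the CBCT before the last beam could count it twice, because that scan follows alignment and later breath-holds.

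The objection does not remove the gap. The one procedure given uses simulation scans, two of them offset, and section 6.3 never mentions the margin although it is a listed endpoint.

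**Conclusion.** The point holds in this form: the margin is linked only to tumor motion, the one stated procedure takes it from four simulation CTs of which two are deliberately offset, and the treatment-day position error is not linked to it. Followed as written, the reported study-level margin may not reflect total tumor position error on treatment days.

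No single size can be given. The assumed ranges run from a 2% to a 55% shortfall for the omitted term, and from 14% to 91% inflation for pooled offsets at a 1.5 mm SD. These rest on independent errors and a margin proportional to SD.

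A reader might go on to infer that trial patients would be treated with inadequate margins. The documents do not support that, because 5.2.2 leaves each patient's margin to the physician. The consequence is for the margin reported under 2.4.2 and for any later trial that uses it. It is worth correcting, because a better source is already being collected.

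**What to change.** Reword 2.2.1, 5.2.2 and 6.3 as follows.

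- Estimate the study-level margin from treatment-day tumor position error relative to plan: the post-alignment CBCT error in 5.2.8, including the CBCT before the last beam. State the formula and its components.
- Split that error into between-patient and within-patient parts. Do not add hold-to-hold variation that it already contains.
- Report same-level simulation motion as a separate component.
- Keep the two offset CTs out of the repeatability estimate and use them only for the level-position relation that 4.1 assigns to them.
- Give the estimate with its uncertainty for the number of patients who contribute treatment-day data, 10 at most.

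The physician's choice of each patient's treatment margin stays as it is, and no margin value is proposed here. The change needs no new scan, visit or patient. It costs revised wording, slightly more analysis, and a reported margin that may turn out larger.

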2.3 Exploratory Objectives

2.3.1 To quantify SBRT dose variation between planned and delivered with VRT-DIBH technique.

2.3.2 Treatment time

2.4 Endpoints

2.4.1 VRT-DIBH feasibility

2.4.2 To determine target margin in VRT-DIBH lung/liver SBRT

2.4.3 To determine threshold used for surface monitoring in VRT-DIBH assisted lung/liver SBRT

3.0 PATIENT ELIGIBILITY

Eligibility waivers are not permitted. Subjects must meet all of the inclusion and exclusion criteria to be registered to the study. Study treatment may not begin until a subject is registered.

3.1 Inclusion Criteria

3.1.1 Patients must be willing and capable to provide informed consent to participate in the protocol.

3.1.2 Patient with presumed pulmonary function capable of holding breath for at least 30 seconds – later to be confirmed.

3.1.3 All men, as well as women of child-bearing potential must agree to use adequate contraception (hormonal or barrier method of birth control; abstinence) **prior to study entry, and until study imaging is complete**. Should a woman become pregnant or suspect she is pregnant while participating in this study, she should inform her treating physician immediately.

3.1.6.1 A female of child-bearing potential is any woman (regardless of sexual orientation, marital status, having undergone a tubal ligation, or remaining celibate by choice) who meets the following criteria:

- Has not undergone a hysterectomy or bilateral oophorectomy; or
- Has not been naturally postmenopausal for at least 12 consecutive months (i.e., has had menses at any time in the preceding 12 consecutive months).

3.1.4 Patients must be compliant to all required pretreatment evaluations (section 5.1)

3.2 Exclusion Criteria

- 3.2.1 Pregnant or lactating women, as treatment involves unforeseeable risks to the embryo or fetus
- 3.2.2 Patients are not compliant to all required pretreatment evaluations (section 5.1).

4.0 TREATMENT PLAN

4.1 Treatment Dosage and Administration

Patient recruit on this treatment protocol will go through training-screening sessions:

1. Patient will go through a tumor motion evaluation session. Since we would like to test the effectiveness of our proposed motion management strategy, we would like to recruit patient with tumor motion in one direction is larger than 5 mm. Tumor motion in free-breathing mode will be evaluated under imaging study..
2. Patient will go through a pre-oxygenation training-screening session. Research studies^{18, 19} already shown that pre-oxygenation can effectively prolong breath-holds in patients with cancer. In this study we will combine patient training, screening, and pre-oxygenation to prolong patient breath-hold duration in radiotherapy procedure. Patient will be asked to breathing oxygen-enhanced air through a facial mask and take deep inspiration breath hold. We will use spirometer to find the maximum deep inspiration breath level and set a comfortable/optimal breath hold level ~75% of the maximum deep inspiration. Only patient can have single DIBH duration \geq 30 seconds will be eligible for the study.
3. Patient will go through a real-time coaching training session assisted by DIBH technique. After being trained, patient will go through motion assessment section. Patient will be set on treatment couch with chest exposed which allows cameras catch patient body surface information. Spirometer will be used to assist DIBH setup. Optical camera system will be used to acquire patient chest/abdomen surface. During the surface image acquisition, imaging will be used to acquire tumor position or diaphragm position. The surface images and tumor positions acquired in single DIBH durations will be used to quantify intra-DIBH patient surface and tumor position stability. The surface images and tumor positions acquired across several DIBH durations will be used to quantify inter-DIBH patient surface and tumor position repeatability. The intermittent time between DIBH durations can be varied between 1-10 minutes.
4. Only patient with inter/intra-DIBH tumor position variation \leq 5 mm and inter/intra-DIBH surface level variation \leq 5 mm will be move on for this VRT-DIBH protocol study. Otherwise, patients will be off study and treated per standard of care.

DIBH qualified patient will experience one high-resolution CT scan as SOC and additional lower dose CT scans to further investigate inter-DIBH patient surface and tumor position stability and repeatability.

1. Spirometer will be used to select DIBH level and monitor DIBH status during CT simulation. One SOC high-resolution CT will be acquired in single DIBH duration. Within 10 minute, a low-resolution/low-dose CT image in single DIBH duration will be acquired. This study is to quantify inter-DIBH tumor position and patient surface repeatability.
2. Patient will then be scanned using a lower dose CT protocol with DIBH level set at $\pm 10\%$ deviated from the selected DIBH level. This study is to find the correlation between DIBH level and tumor position /chest-abdomen surface level.

The SOC DIBH CT scan will be transferred to Eclipse treatment planning system for treatment planning. Tidal volume measured by spirometer and DIBH surface from CT image will be used as a reference surface for patient treatment initial setup. CBCT will be acquired before each fractional treatment for the patient alignment before beam delivery.

During the treatment delivery, patient will perform DIBH while AlignRT system monitors patient surface. As a pilot study, we will also use spirometer to monitor patient breath-hold tidal volume, and imaging acquired in any two DIBH periods to quantify inter- and intra- DIBH tumor position variation. Following our SBRT treatment protocol, patient will get CBCT scan before the last beam delivery. We will follow the same protocol to acquire CBCT images. These CBCT images will be used to evaluate treatment dose variation to quantify treatment delivery accuracy.

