5.2 Procedures during Treatment

5.2.1 CT simulation

- CT Simulation scans at DIBH will be assisted by spirometer ---must ensure tubing from spirometer not over chest wall so skin rendering is able to be reproduced.
- CT simulation scan (full-length) will be acquired with at a single DIBH duration, starting at least 10 cm above the superior extent of tumor and continuing on every CT slice to at least 10 cm below the inferior extent of the tumor. DIBH signal will be monitored by spirometer. If there is no contraindication to contrast administration, patient will receive DIBH CT scans with contrast administration.
- CT acquisition should be done with gantry 0 degree with spacing ≤ 2 mm.
- Additional DIBH CT scans will be conducted using lower dose CT scan protocol. One at the same DIBH level and the other two will be $\pm 10\%$ deviated from DIBH breath level

- All images will be transferred to the treatment planning computers for tumor motion evaluation and planning.

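### The ±10% breath-hold CTs are tied only to a correlation with spirometer level: no tumor-on-surface slope and no +10%/−10% scan order are specified for the surface threshold in 2.2.2

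*Combined protocol and SAP*

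**What the plan says.** Each qualified patient has four breath-hold CTs. Section 4.1 starts with the standard-of-care scan, followed by a repeat at the same level: "Within 10 minute, a low-resolution/low-dose CT image in single DIBH duration will be acquired". It continues: "Patient will then be scanned using a lower dose CT protocol with DIBH level set at" 10% either side of the selected level. Section 5.2.1 agrees, describing the additional scans as "One at the same DIBH level and the other two will be" 10% off that level, and section 5.2.2 confirms the total: "On the acquired four different DIBH CTs, gross tumor volume (GTV) will be contoured by an appropriately trained physician".

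The purpose of the deviated scans is given once, in 4.1: "This study is to find the correlation between DIBH level and tumor position /chest-abdomen surface level". The level is the spirometer level. Which of +10% and −10% comes first is not stated.

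The secondary objective these scans can serve is 2.2.2: "To determine VRT surface monitoring threshold by investigating inter/intra VRT-DIBH patient surface stability/reproducibility/sensitivity". The threshold is also listed as endpoint 2.4.3. Sensitivity is not defined and has no unit.

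The analyses named elsewhere do not fill the gap:

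- Section 5.2.2, on the same four CTs: "Both inter- and intra- motion amplitude will be analyzed and margins will be estimated".
- Section 5.2.8 covers surface stability and reproducibility during treatment.
- Section 6.2 covers descriptive statistics on stability, repeatability and dose deviation in 10 patients.
- Section 6.3 covers CBCT images only.

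**The concern.** Section 1.3 explains that the beam is enabled when the surface lies within a threshold of its reference position. To judge a threshold in mm, one needs to know how far the tumor moves when the surface moves by a given number of mm. The ±10% scans are the only deliberate perturbation in the study, so they are the natural place to learn this. A correlation does not supply it. It has no units, its stated axis is spirometer level rather than surface position, and with four points per patient it is very imprecise. If coefficients were computed on data pooled over patients, anatomical differences between patients would be mixed in as well.

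The open +/− order is a separate weakness. If staff settle into one sequence, any steady drift over the session is read as an effect of level, and averaging over patients does not remove it. The low-dose CTs are additional imaging obtained for research, so they should yield a quantity that the threshold decision can use.

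**Working it through.** **Plan's own figure.** 1 standard-of-care scan + 1 low-dose repeat + 2 deviated scans = 4 scans, at 3 levels (0, 0, +, −). This matches section 5.2.2.

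**Correlation with n = 4.**

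- With no relation, r is uniform on −1 to 1. So P(|r| ≥ 0.8) = 0.20 and P(|r| ≥ 0.9) = 0.10.
- Two-sided p < 0.05 needs |r| > t/√(t² + 2) with t = 4.303 on 2 df, which is 0.950.
- The Fisher interval is tanh(atanh r ± 1.96/√(n − 3)). For r = 0.90 it is −0.45 to 0.998; for r = 0.95 it is −0.13 to 0.999.
- Units: in one simulated patient (levels 0, 0, +3, −3 mm), multiplying tumor displacement by 0.3, 1 and 2 leaves r at 0.993 each time, while the slope is 0.34, 1.14 and 2.27. The coefficient cannot tell these apart.

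**What a slope from the same scans would give.** Assumptions, not in the documents: residual SD s of 1 to 2 mm, and surface change D of 2 to 5 mm per 10% step.

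- One patient: SE = s/(D√2), 2 residual df. With s = 1 and D = 3, SE = 0.236 and the 95% half-width is 4.303 × 0.236 = 1.01 mm/mm. Over the assumed ranges it is 0.61 to 3.04.
- Pooled over 10 patients, with patient-specific intercepts and a common slope: SE = 0.236/√10 = 0.075 on 3 × 10 − 1 = 29 df, half-width 0.15. Over the ranges it is 0.09 to 0.46.
- If true slopes vary between patients with SD 0.3 to 0.5 (assumed), the half-width for the mean slope is 0.24 to 0.62.
- If only 5 patients reach CT: 0.14 to 0.68 with a common slope, 0.41 to 1.08 with varying slopes.

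**Scan order.** The linear slope per 10% step is (y₊ − y₋)/2. The reference scans sit at the centre of the level range and have zero weight.

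- Step shift c between the reference and deviated scans: (c − c)/2 = 0. No bias.
- Linear drift d per scan, order 0, 0, +, −: (3d − 4d)/2 = −d/2. Order 0, 0, −, +: +d/2. Only the +/− order sets the sign.
- Relative size, assuming a true 4 mm from +10% to −10% (2 mm per step): d = 0.2 mm gives 0.1/2 = 5%; d = 1 mm gives 0.5/2 = 25%.
- Curvature: mean of deviated scans minus mean of reference scans is 3.5d − 1.5d = 2d. Taking the reference scans first therefore mixes drift into a quadratic term, though not into the slope.
- Adjusting afterwards: a linear time term removes the slope bias and raises the slope variance only from 0.500 to 0.556 (in units of s² per step²). It leaves 1 residual df per patient and assumes no curvature, because intercept, slope, curvature and time together use all four points.

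**The case against.** The best counter-argument is that section 4.1 states an aim, not a statistic. *Correlation* may simply mean *relationship*; no coefficient, test or pooling is named, and sections 6.0 and 6.2 promise only descriptive statistics. That is a fair reading, so it cannot be said that the plan commits to a coefficient. But on that reading no analysis of the relationship is specified anywhere, and the point stands as a gap in the analysis text.

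Second, section 5.2.2 has the tumor center located on all four CTs and motion amplitude analyzed. The size of the tumor shift would therefore be seen, and a high correlation could not entirely hide a trivial or a large shift. This stands. What 5.2.2 does not provide is tumor shift relative to surface shift.

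Third, the drift percentages rest on figures absent from the documents, and they require both a habitual order and drift in the same direction across patients. Neither is documented. The percentages show a possible size, not an expected one.

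A reader might also infer more than the documents support:

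- *The experiment cannot give a sensitivity.* This is true of the coefficient but not of the scans, which yield a slope.
- *Taking the reference scans first biases the result.* It does not bias the linear slope.
- *These CTs are the only source on tumor versus surface.* Section 4.1 also records both at the motion assessment and during treatment. Those breath-holds aim to reproduce one level, and screening keeps only patients within 5 mm, so they span a narrow range; but they exist.
- *The protocol requires mm per mm.* This is a reasonable reading of an undefined term, not the protocol's wording.

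**Conclusion.** The point holds as a gap in analysis and scan order. The only stated use of the ±10% scans is a correlation with spirometer level. A coefficient from four scans is close to uninformative within a patient and has no units, and no section specifies how tumor shift is to be related to surface shift. Sensitivity in 2.2.2 therefore has no defined analysis behind it.

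The unspecified +/− order leaves room for a slope bias of half the per-scan drift per 10% step, or 5% to 25% under the assumed drift of 0.2 to 1 mm and the assumed 4 mm difference. It arises only with a habitual order and drift in a common direction.

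The primary feasibility objective is not affected. The change is worth making because it is cheap and because an order effect is harder to separate once the scans are done.

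**What to change.** In section 4.1 (CT item 2) and section 6.3:

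- Replace the correlation by within-patient slopes: mm of tumor shift and mm of surface shift per 10% of level, and mm of tumor per mm of surface. State that the last of these is what sensitivity means in 2.2.2.
- Report each patient's slopes. Summarise over patients with patient-specific intercepts and a 95% interval from the pooled within-patient residuals, described as exploratory. Note that this interval assumes a common slope; the listed individual slopes show whether that is plausible.
- Do not use the two same-level scans alone as the error term. One is high-resolution and the other low-dose, and the pair gives only 1 df per patient.
- Alternate the order of the +10% and −10% scans over the patients who reach CT, and record the order. Drift common to all patients then cancels in the pooled slope when the two orders are balanced; each single patient's slope still carries it.

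The cost is a few lines of analysis text and a short order list, with no added scans. Per-patient intervals will be wide (half-width about 0.6 to 3 mm/mm under the assumptions above) and should be presented as such.
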